10.2.12.1 Non-infectious Pneumonitis

Non-infectious pneumonitis is a class effect of rapamycin derivatives, including everolimus. In the randomized study, non-infectious pneumonitis was reported in 14% of patients treated with everolimus. The incidence of CTCAE grade 3 and 4 non-infectious pneumonitis was 4% and 0%, respectively. Fatal outcomes have been observed.

Consider a diagnosis of non-infectious pneumonitis in patients presenting with non-specific respiratory signs and symptoms such as hypoxia, pleural effusion, cough, or dyspnea, and in whom infectious, neoplastic, and other causes have been excluded by means of appropriate investigations. Advise patients to report promptly any new or worsening respiratory symptoms.

Patients who develop radiological changes suggestive of non-infectious pneumonitis and have few or no symptoms may continue everolimus therapy without dose alteration. If symptoms are moderate, consider interrupting therapy until symptoms improve. The use of corticosteroids may be indicated. Everolimus may be reintroduced at 5 mg daily.

For cases where symptoms of non-infectious pneumonitis are severe, discontinue everolimus therapy and the use of corticosteroids may be indicated until clinical symptoms resolve. Therapy with everolimus may be re-initiated at a reduced dose of 5 mg daily depending on the individual clinical circumstances.

10.2.12.2 Infections

Everolimus has immunosuppressive properties and may predispose patients to infections, especially infections with opportunistic pathogens. Localized and systemic infections, including pneumonia, other bacterial infections and invasive fungal infections, such as aspergillosis or candidiasis, have occurred in patients taking everolimus. Some of these infections have been severe (e.g., leading to respiratory failure) or fatal. Physicians and patients should be aware of the increased risk of infection with everolimus, be vigilant for signs and symptoms of infection and institute appropriate treatment promptly. Complete treatment of pre-existing invasive fungal infections prior to starting treatment with everolimus. If a diagnosis of invasive systemic fungal infection is made, discontinue everolimus and treat with appropriate antifungal therapy.

Reactivation of Hepatitis B (HBV) has been observed in patients with cancer receiving chemotherapy. Sporadic cases of Hepatitis B reactivation have also been seen in this setting with everolimus. Use of antivirals during anti-cancer therapy has been shown to reduce the risk of Hepatitis B virus reactivation and associated morbidity and mortality. A detailed assessment of Hepatitis B/C medical history and risk factors must be done for all patients at screening, with testing performed prior to the first dose of everolimus.

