3.3.1.2 Non-hematologic Toxicity

Dose Modifications

Based on **sorafenib or everolimus** -Related Non-Hematologic Toxicities:

CTCAEv.4 Grade	% of Dose Planned
0-2+	100%+
3*	hold**
4	hold***

+For symptomatic Grade 2 toxicity, the suspect drug dose may be held at the discretion of the local investigator until recovery to CTCAE Grade 0-1, then resume at one dose lower.

*Except nausea/vomiting (unless patients are on optimal antiemetic therapy)

**Hold suspect drug until recovery to CTCAE Grade 0-1 (or to within 1 grade of starting values for pre-existing laboratory abnormalities), and then resume at one dose level lower.

***Hold suspect drug until recovery to CTCAE Grade 0-1 (or to within 1 grade of starting values for pre-existing laboratory abnormalities), and then resume at two dose levels lower.

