3.3.3 Management of stomatitis/oral mucositis/mouth ulcers

CTCAE v 4.0 grade 1-2 stomatitis/oral mucositis/mouth ulcers due to everolimus should lead to using local supportive care such as use of mouthwash (avoid those containing alcohol). The use of topical high potency steroids such as triamcinolone oral paste 0.1% (Kenalog in Orabase®) is allowed. Please refer to section 3.3.1.2 for dose modifications. Suggested guidelines for treatment of stomatitis/oral mucositis/mouth ulcers:

1. For mild toxicity (grade 1), use conservative measures such as non-alcoholic mouth wash or salt water (0.9%) mouth wash several times a day until resolution.
2. For more severe toxicity (grade 2 in which case patients have pain but are able to maintain adequate oral alimentation, or grade 3 in which case patients cannot maintain adequate oral alimentation), the suggested treatments are topical analgesic mouth treatments (e.g., local anesthetics such as benzocaine, butyl aminobenzoate, tetracaine hydrochloride, menthol, or phenol) with or without topical corticosteroids, such as triamcinolone oral paste 0.1% (Kenalog in Orabase®).

3. Agents containing hydrogen peroxide, iodine, and thyme derivatives may tend to worsen mouth ulcers. It is preferable to avoid these agents.
4. Antifungal agents must be avoided unless a fungal infection is diagnosed. In particular, systemic imidazole antifungal agents (ketoconazole, fluconazole, itraconazole, etc.) should be avoided in all patients due to their strong inhibition of everolimus and sorafenib metabolism, therefore leading to higher everolimus exposures. Therefore, topical antifungal agents are preferred if an infection is diagnosed. Similarly, antiviral agents such as acyclovir should be avoided unless a viral infection is diagnosed.

Note: Stomatitis/oral mucositis should be appropriately graded using the functional grading given on the NCI-CTCAE, version 4.0.

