3.3.7 Management of suspected everolimus toxicity

Table 3-7: Criteria for dose-modification in case of suspected everolimus toxicity and re-initiation of everolimus treatment

Toxicity	Actions

Non-hematological toxicity
 
Grade 2 (except pneumonitis – refer to Table 3-6)
 
Grade 3 (except hyperlipidemia*) (except pneumonitis – refer to Table 3-6)
 
Grade 4
	
If the toxicity is tolerable to the patient, maintain the same dose. If the toxicity is intolerable to patient, interrupt everolimus until recovery to grade ≤1. Then reintroduce everolimus at same dose. If event returns to grade 2, then interrupt everolimus until recovery to grade ≤1. Then reintroduce everolimus at same dose level.
 
Interrupt everolimus until recovery to grade ≤1. Then reintroduce everolimus at same dose level. For pneumonitis consider the use of a short course of corticosteroids.
 
Discontinue everolimus.

Hematological toxicity
 
Grade 2 Thrombocytopenia (platelets <75, ≥ 50x10⁹/L)
 
Grade 3 Thrombocytopenia (platelets <50, ≥ 25 x10⁹/L)
 
Grade 4 Thrombocytopenia (platelets < 25 x10⁹/L)
	
Interrupt everolimus until recovery to grade ≤1 (>75 x10⁹/L). Then reintroduce everolimus at initial dose. If thrombocytopenia again returns to grade 2, interrupt everolimus until recovery to grade ≤1. Then reintroduce everolimus at same dose level.
 
Interrupt everolimus until recovery to grade ≤1 (platelets ≥ 75 x10⁹/L). Then resume everolimus at same dose level. If grade 3 thrombocytopenia recurs, discontinue everolimus.
 
Discontinue everolimus.

Toxicity	Actions
Grade 3 Neutropenia (neutrophils $<1, \geq 0.5 \times 10^9/L$)	Interrupt everolimus until recovery to grade ≤ 1 (neutrophils $\geq 1.5 \times 10^9/L$). Then resume everolimus at the initial dose. If ANC again returns to Grade 3, hold everolimus until the ANC $\geq 1.5 \times 10^9/L$. Then resume everolimus dosing at same dose level. Discontinue patient from study therapy for a third episode of grade 3 neutropenia.
Grade 4 Neutropenia (neutrophils $< 0.5 \times 10^9/L$)	Interrupt everolimus until recovery to grade ≤ 1 (neutrophils $\geq 1.5 \times 10^9/L$). Then resume everolimus at the lower dose level. If grade 3 or grade 4 neutropenia occurs despite this dose reduction, discontinue everolimus.

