10.2.10.1.1 Agents that may Increase Everolimus Blood Concentrations

CYP3A4 Inhibitors and Pgp Inhibitors: In healthy subjects, compared to everolimus treatment alone there were significant increases in everolimus exposure when everolimus was co-administered with:

- ketoconazole (a strong CYP3A4 inhibitor and a Pgp inhibitor) - Cmax and AUC increased by 3.9- and 15.0-fold, respectively.
- erythromycin (a moderate CYP3A4 inhibitor and a Pgp inhibitor) - Cmax and AUC increased by 2.0- and 4.4-fold, respectively.
- verapamil (a moderate CYP3A4 inhibitor and a Pgp inhibitor) - Cmax and AUC increased by 2.3- and 3.5-fold, respectively.

Concomitant strong or moderate inhibitors of CYP3A4 and Pgp inhibitors should not be used.

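### Section 10.2.12.2 discontinues everolimus when an invasive systemic fungal infection is diagnosed, but the toxicity rules in 3.3 have no such exception and, read literally, allow it to continue or restart

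*Combined protocol and SAP*

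**What the plan says.** All references are to the combined protocol and SAP.

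- **10.2.12.2 (Infections).** On invasive fungal disease the instruction is: "If a diagnosis of invasive systemic fungal infection is made, discontinue everolimus and treat with appropriate antifungal therapy". The trigger is the diagnosis. No grade is named and no restart is described. The same section says of infections under everolimus: "Some of these infections have been severe (e.g., leading to respiratory failure) or fatal".
- **3.3.7, Table 3-7 (suspected everolimus toxicity, non-hematological rows).** At grade 2: "If the toxicity is tolerable to the patient, maintain the same dose". If it is not tolerable, everolimus is interrupted and brought back at the same dose; if grade 2 recurs, the row says "interrupt everolimus until recovery to grade ≤1. Then reintroduce everolimus at same dose level". At grade 3, after interruption and recovery: "Then reintroduce everolimus at same dose level. For pneumonitis consider the use of a short course of corticosteroids". At grade 4, and for any interruption of 3 weeks or more, everolimus is discontinued. The named exceptions are pneumonitis, which is sent to Table 3-6, and grade 3 hyperlipidemia.
- **3.3.1.2 (Non-hematologic Toxicity).** Grades 0-2 receive 100% of the dose, with an optional hold for symptomatic grade 2. At grade 3 the suspect drug is held until recovery, "and then resume at one dose level lower". At grade 4 it is held and resumed two levels lower. The only named exception is nausea and vomiting.

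Neither Table 3-7 nor 3.3.1.2 mentions fungal or any other infection, and neither points to 10.2.12.2.

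**The concern.** An investigator managing a suspected everolimus toxicity is directed by 3.3.1 to Tables 3-6 and 3-7. A reader of Table 3-7 sees a short list of exceptions, does not find infection on it, and applies the general rows. For a grade 2 or grade 3 event those rows keep the patient on everolimus or bring the patient back to it. An investigator who reads the drug-information section stops the drug. Both are following the protocol.

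Other everolimus warnings were carried forward into section 3.3. Pneumonitis (10.2.12.1) has Table 3-6 and an exception clause in Table 3-7. Hepatitis B reactivation, which sits in 10.2.12.2 beside the fungal instruction, has section 3.3.2. The fungal instruction has no counterpart. At stake is continued or renewed exposure to an immunosuppressive drug during or after an infection that the protocol itself describes as sometimes severe or fatal.

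**Working it through.** The plan gives no figure to reproduce here. The check is a comparison of texts, followed by a short calculation of how often the event might arise.

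**Step 1. Compare by grade.** Assume the infection is attributed to a study drug, since 3.3 and 3.3.1.2 apply only to related toxicity and Table 3-7 only to suspected everolimus toxicity.

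| Situation | 10.2.12.2 | Table 3-7 | 3.3.1.2 |
|---|---|---|---|
| Grade 2 | Discontinue | Same dose if tolerable; otherwise interrupt, then same dose | Full dose; optional hold if symptomatic, then one lower |
| Grade 3 | Discontinue | Interrupt, then same dose level | Hold, then one level lower |
| Grade 4 | Discontinue | Discontinue | Hold, then two levels lower |
| Interruption of 3 weeks or more | Discontinue | Discontinue | No such row |

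Table 3-7 therefore departs from 10.2.12.2 at grades 2 and 3 and agrees with it in the last two rows. Section 3.3.1.2 departs from it at grades 2, 3 and 4.

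**Step 2. Separate continuing from restarting.** Keeping the dose at a tolerable grade 2 (Table 3-7), or at grade 2 without a hold (3.3.1.2), contradicts an instruction to discontinue on any meaning of that word. Restarting after recovery contradicts it only if discontinuation is permanent. Section 10.2.12.2 does not say so. The neighbouring 10.2.12.1 uses the same verb for severe pneumonitis and then expressly permits re-initiation. Section 10.2.12.2 contains no such permission, but its silence is not a prohibition.

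**Step 3. Check what a lower dose level means for everolimus.** In Table 3-2 everolimus is 5 mg daily at levels 1, -1 and -2; only sorafenib falls. For everolimus, the grade 3 restart in 3.3.1.2 is therefore the same 5 mg as in Table 3-7. The difference between those two at grade 3 is nominal for this drug.

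**Step 4. Frequency.** Inputs: section 10.2.12.8 lists aspergillosis and candidiasis each at under 1%. Section 2.4 shows Groups A and C closed and Group B open, and section 7.2 sets Group B at a maximum of 32 patients.

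- Each organism: fewer than 0.01 × 32 = 0.32 expected cases.
- Both together, taking the two ceilings as additive: fewer than 0.02 × 32 = 0.64.

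This assumes that the listed rates carry over to this population and combination. The listing does not restrict candidiasis to invasive disease, which would make the figure too high for the event in question. Patients here may take up to 16 mg of dexamethasone daily and also take sorafenib, and the documents do not say how that changes the rate.

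**The case against.** The strongest reply is that there is no contradiction, only a specific rule and two general ones. Section 10.2.12.2 names the event and is triggered by diagnosis; Table 3-7 and 3.3.1.2 are generic and never mention fungal infection. A sensible investigator would let the specific text govern. Other provisions also narrow the room for a restart: 3.3.1 takes a patient off study, or to study PI review, when toxicity lasts beyond 2 weeks, and 3.7.1 removes patients for unacceptable toxicity, incapacitating illness or a toxicity delay of more than 21 days. The documents do not say how this event would be graded, so the grade 2 case may be uncommon.

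Much of this stands, and it limits the size of the point. It does not remove it. No order of precedence is stated, the operative table lists its exceptions without this one, and a warning in the same section (hepatitis B) did receive operative rules.

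A reader might infer more than the documents support:

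- **A clash over antifungal treatment.** Section 3.3.3 says "systemic imidazole antifungal agents (ketoconazole, fluconazole, itraconazole, etc.) should be avoided in all patients", while 10.2.12.2 calls for antifungal therapy. But 3.3.3 is stomatitis guidance, its advice on antifungals opens with an exception for diagnosed fungal infection, and its stated reason is mainly higher everolimus exposure. Section 10.2.12.2 stops everolimus first and does not name an azole. Sections 10.2.10.1.1, 10.2.10.1.2 and 10.2.12.7 already restrict CYP3A4 inhibitors with everolimus, and 10.2.10.1.2 requires asking about new medications at each visit.
- **A specific overexposure on restart.** It is tempting to multiply the 5 mg dose by the 15.0-fold AUC rise reported with ketoconazole. The result, 15 × 5 = 75 mg, lies outside the 5-70 mg range over which 10.2.13 states AUC proportionality. The rise was measured in healthy subjects, and the combination is one the plan says not to use.
- **Divergence between sites, or bias in PFS3 or PFS6.** Section 9.4 says subjects at non-NCI sites were off treatment by Amendment C, and fewer than one expected case cannot materially move a PFS rate.

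**Conclusion.** The point holds as a narrow safety contradiction. For a drug-attributed invasive fungal infection, 10.2.12.2 discontinues everolimus at any grade. Table 3-7 at grade 2 and 3.3.1.2 at grade 2 permit continuing; Table 3-7 after grades 2 and 3, and 3.3.1.2 after grades 3 and 4, permit a restart. The conflict with continuing is definite. The conflict with restarting is conditional on discontinuation being permanent, which the text leaves open. It would be wrong to say that Table 3-7 opposes 10.2.12.2 throughout, because it agrees at grade 4 and for interruptions of 3 weeks or more.

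The event is rare, with fewer than 0.32 expected cases of each listed fungal infection in 32 patients if the listed rates apply, so the primary endpoints are not at issue. The consequence for an individual patient can be serious and the repair is nearly free, so the passages should be reconciled. Table 3-7 and 3.3.1.2 also differ from each other more generally, most plainly at grade 4 (discontinue versus resume two levels lower). That mismatch is not confined to fungal infection. No view is taken on which clinical rule is right.

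**What to change.** The sponsor should reconcile 10.2.12.2, 3.3.1.2 and Table 3-7 and place the single reconciled rule for invasive systemic fungal infection in Table 3-7. It can be a separate row or an exception clause with a cross-reference, as already done for pneumonitis. The rule should state whether discontinuation of everolimus is permanent. Sections 3.3.1.2 and 10.2.12.2 should then point to that entry so that only one text governs. The choice of rule belongs to the sponsor and its clinical advisers.

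The cost is one table entry and two cross-references in the next amendment. It needs no additional patients, visits or procedures, and it does not touch the statistical design.

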10.2.12.3 Oral Ulceration

Mouth ulcers, stomatitis, and oral mucositis have occurred in patients treated with everolimus. In the randomized study, approximately 44% of everolimus treated patients developed mouth ulcers, stomatitis, or oral mucositis, which were mostly CTCAE grade 1 and 2. In such cases, topical treatments are recommended, but alcohol- or peroxide-containing mouthwashes should be avoided as they may exacerbate the condition. Antifungal agents should not be used unless fungal infection has been diagnosed.

10.2.12.4 Renal Function

Elevations of serum creatinine, usually mild, have been reported in clinical trials. Monitoring of renal function, including measurement of blood urea nitrogen (BUN) or serum creatinine, is recommended prior to the start of everolimus therapy and periodically thereafter.

10.2.12.5 Blood Glucose and Lipids

Hyperglycemia, hyperlipidemia, and hypertriglyceridemia have been reported in clinical trials. Monitoring of fasting serum glucose and lipid profile is recommended prior to the start of everolimus therapy and periodically thereafter. When possible, optimal glucose and lipid control should be achieved before starting a patient on everolimus.

10.2.12.6 Hematological Parameters

Decreased hemoglobin, lymphocytes, neutrophils, and platelets have been reported in clinical trials. Monitoring of complete blood count is recommended prior to the start of everolimus therapy and periodically thereafter.

10.2.12.7 CYP3A4 Interactions

Due to significant increases in exposure of everolimus, co-administration with strong or moderate inhibitors of CYP3A4 (e.g., ketoconazole, itraconazole, clarithromycin, atazanavir, nefazodone, saquinavir, telithromycin, ritonavir, amprenavir, indinavir, nelfinavir, delavirdine, fosamprenavir, voriconazole, aprepitant, erythromycin, fluconazole, grapefruit juice, verapamil or diltazem) or P-glycoprotein (PgP) should be avoided.

Everolimus is a substrate of CYP3A4, and also a substrate and moderate inhibitor of the multidrug efflux pump PgP. In vitro, everolimus is a competitive inhibitor of CYP3A4 and a mixed inhibitor of CYP2D6.

10.2.12.7.1 Agents that may Increase Everolimus Blood Concentrations CYP3A4 Inhibitors and PgP Inhibitors:

In healthy subjects, compared to everolimus treatment alone there were significant increases in everolimus exposure when everolimus was coadministered with:

- ketoconazole (a strong CYP3A4 inhibitor and a PgP inhibitor) - C_{max} and AUC increased by 3.9- and 15.0-fold, respectively.
- erythromycin (a moderate CYP3A4 inhibitor and a PgP inhibitor) - C_{max} and AUC increased by 2.0- and 4.4-fold, respectively.
- verapamil (a moderate CYP3A4 inhibitor and a PgP inhibitor) - C_{max} and AUC increased by 2.3- and 3.5-fold, respectively.

Concomitant strong or moderate inhibitors of CYP3A4 and P-gP inhibitors should not be used.

10.2.12.7.2 Agents that may Decrease Everolimus Blood Concentrations CYP3A4 Inducers:

In healthy subjects, co-administration of everolimus with rifampin, a strong inducer of CYP3A4, decreased everolimus AUC and C_{max} by 64% and 58% respectively, compared to everolimus treatment alone. Consider a dose increase of everolimus when co-administered with strong inducers of CYP3A4 or P-gP if alternative treatment cannot be administered.

10.2.12.7.3 Agents whose Plasma Concentrations may be Altered by Everolimus

Studies in healthy subjects indicate that there are no clinically significant pharmacokinetic interactions between everolimus and the HMG-CoA reductase inhibitors atorvastatin (a CYP3A4 substrate) and pravastatin (a non-CYP3A4 substrate) and population pharmacokinetic analyses also detected no influence of simvastatin (a CYP3A4 substrate) on the clearance of everolimus.

10.2.12.8 Adverse Reactions

Because clinical trials are conducted under widely varying conditions, the adverse reaction rates observed cannot be directly compared to rates in other trials and may not reflect the rates observed in clinical practice.

The data described below reflect exposure to everolimus (n=274) and placebo (n=137) in a randomized, controlled trial in patients with metastatic renal cell carcinoma who received prior treatment with sunitinib and/or sorafenib. The median age of patients was 61 years (range 27-85), 88% were Caucasian, and 78% were male. The median duration of blinded study treatment was 141 days (range 19-451) for patients receiving everolimus and 60 days (range 21-295) for those receiving placebo.

The most common adverse reactions (incidence $\geq 30\%$) were stomatitis, infections, asthenia, fatigue, cough, and diarrhea. The most common grade 3/4 adverse reactions (incidence $\geq 3\%$) were infections, dyspnea, fatigue, stomatitis, dehydration, pneumonitis, abdominal pain, and asthenia. The most common laboratory abnormalities (incidence $\geq 50\%$) were anemia, hypercholesterolemia, hypertriglyceridemia, hyperglycemia, lymphopenia, and increased creatinine. The most common grade 3/4 laboratory abnormalities (incidence $\geq 3\%$) were lymphopenia, hyperglycemia, anemia, hypophosphatemia, and hypercholesterolemia. Deaths due to acute respiratory failure (0.7%), infection (0.7%) and acute renal failure (0.4%) were observed on the everolimus arm but none on the placebo arm. The rates of treatment-emergent adverse events (irrespective of causality) resulting in permanent discontinuation were 14% and 3% for the everolimus and placebo treatment groups, respectively. The most common adverse reactions (irrespective of causality) leading to treatment discontinuation were pneumonitis and dyspnea.

Infections, stomatitis, and pneumonitis were the most common reasons for treatment delay or dose reduction. The most common medical interventions required during everolimus treatment were for infections, anemia, and stomatitis.

Likely (occurring in more than 20% of patients)

Adverse events most frequently observed with everolimus are rash, stomatitis/oral mucositis, fatigue, anorexia, nausea, diarrhea, peripheral edema, asthenia, cough, dyspnea, ocular toxicity and infections. Infections include nasopharyngitis (6%), pneumonia (6%), urinary tract infection (5%), bronchitis (4%), sinusitis (3%), aspergillosis (<1%), candidiasis (<1%), and sepsis (<1%).

Laboratory abnormalities include anemia, neutropenia, thrombocytopenia, lymphopenia, hypercholesterolemia, and/or hypertriglyceridemia, hyperglycemia, hypophosphatemia, aspartate and alanine transaminase elevation. The majority of these AEs have been of mild to moderate severity (CTCAE grade 1-2).

Common (occurring in 3 – 20% of Patients)

Adverse events occurring in 3-20% of patients include vomiting, pyrexia, mucosal inflammation, epistaxis, pneumonitis (includes pneumonitis, interstitial lung disease, lung infiltration,, pulmonary alveolar hemorrhage, pulmonary toxicity, and alveolitis), pruritus, dry skin, headache, dysgeusia, pain in extremity, abdominal pain, dry mouth, hemorrhoids, dysphagia, chest pain, chills, pleural effusion, pharyngolaryngeal pain, rhinorrhea, hand-foot syndrome, nail disorder, erythema, onychoclasia, skin lesion, acneiform dermatitis, insomnia, dizziness, paresthesia, eyelid edema, hypertension, renal failure, tachycardia, jaw pain, and hemorrhage.

Laboratory abnormalities include increased bilirubin (<1% grade 3 or 4).

Rare but Serious (occurring in fewer than 3% of patients)

Acute respiratory failure and acute renal failure.

